# 2.3 Primary endpoint

The primary endpoint is the number of bleeding episodes during at least 24 weeks from treatment onset. All treated bleeding episodes will be considered for this endpoint, including bleeding episodes recorded as post-surgical or caused by surgery or other medical or dental procedures.

The endpoint will be analysed when the main part of trial has been completed.

### 2.3.1 Estimand and primary statistical analysis

The estimand for the primary endpoint is the "if all patients had adhered" estimand.

The treatment ratio between prophylaxis s.c. concizumab and on-demand i.v. eptacog alfa (rFVIIa) during at least 24 weeks for all randomised patients if all patients adhered to trial drug and did not initiate alternative treatment options. To initiate alternative treatment options in this respect is defined as stopping concizumab or eptacog alfa on-demand treatment and initiating alternative treatment options.

This estimand is a de jure estimand assessing the expected added benefit a patient can achieve if continuing treatment with prophylactic s.c. concizumab as compared to on-demand i.v. eptacog alfa (rFVIIa) under similar conditions as observed in this trial.

The estimand for the primary endpoint will be estimated using negative binomial regression with log of exposure time in the included observational period of the main part as offset and regimen as factor. The offset for first CPoC criterion of patients in concizumab arm is the log of the individual exposure time at the last dose level reached at the time of analysis excluding the 2 weeks run-in period for subjects on 0.15 mg/kg. The offset for the second criterion of patients in concizumab arm is the log of the individual exposure time in the main part. For patients in the on-demand arm regardless of criterion, the offset is the log of the exposure time in the main part. The analysis provides an estimate of the ABR ratio between regimens (concizumab prophylactic and on-demand eptacog alfa (rFVIIa)) with corresponding 95% confidence interval and also actual estimate of the ABR with corresponding 95% confidence interval for each regimen. This analysis has the underlying assumption that the missing data mechanism is "missing at random", i.e. missing at random (MAR). Under this assumption, the statistical behaviour of the missing data (given the

CONFIDENTIAL

Date: Version: Status: Page:

23 October 2018 | Novo Nordisk 1.0 Final 9 of 16

observed responses and the mean value structure) is assumed to be the same as for the observed data. The estimand will be estimated based on the FAS and only data collected prior to discontinuation of trial product or initiation of alternative treatment options will be used to draw inference.

### 2.3.2 Sensitivity analysis

To evaluate the robustness of the MAR assumption implied in the primary analysis, a modified tipping point analysis will be performed where patients having discontinued before finalization of the main part are assumed to have a worse outcome compared to what was observed during the main part of the trial. This will be done by adding a value  $\Delta$  to the observed bleeding episodes in the main part of the trial of the concizumab patients before analysing the data. The offset is maintained as being the exposure during the main part since it is not possible to identify the amount of missing observation time. The degree of worsening,  $\Delta_i$  will gradually be increased to evaluate at which point concizumab prophylaxis no longer is superior to on-demand eptacog alfa (rFVIIa). The results of the primary analysis will be considered robust if the tipping point is above what is considered clinically plausible.

The second CPoC criterion evaluating the effect of concizumab when given as an escalation regimen includes observations from the 2 week run-in period. In the 2 week run-in period some patients have been allowed to continue on pre-trial prophylaxis treatment and so including this period in the analysis may result in some patients having fewer bleeds in the run-in period. Since this can affect the ABR, an additional sensitivity analysis will be performed where the second CPoC criterion will be evaluated as described for the primary endpoint but without including observations from the 2 week run-in period and using log of exposure time excluding those days as the offset.

The primary endpoint is assessed using all treated bleeding episodes including those recorded as post-surgery or caused by surgical or other medical or dental procedures. Since the inclusion of bleeding episodes recorded as post-surgery or caused by surgical or other medical or dental procedures can affect the ABR, an additional sensitivity analysis will be performed excluding these bleeding episodes from the primary and secondary CPoC criteria.

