### 2 Statistical considerations

All endpoints referring to the time frame of at least 24 weeks will be evaluated in the main part of the trial, defined to end when the last patient has completed a minimum of 24 weeks of treatment or at LPFT (visit 2) + 24 weeks if the last patient has withdrawn before visit 9. Please refer to Figure 2–1 for further information.

Data from when the on-demand treated patients are transferred to concizumab subcutaneous (s.c.) prophylaxis will not be included in this evaluation. Observations from the extension part in the ondemand arm will be summarised separately as well as combined with observations from the main part when reporting the extension part data.

Endpoints comprising number of bleeding episodes will be evaluated based on treated bleeding episodes only. Multiple bleeding locations occurring from the same event (e.g., due to a bicycle accident) or at the same time point will be counted as one bleeding episode. Further, the endpoints will not include re-bleeds.

A re-bleed is defined as a bleeding episode (worsening of bleeding site conditions e.g. swelling, pain) within 72 hours after stopping treatment of a previous bleeding episode at the same (or subset of the same) anatomical location. If a bleeding episode occurs in the same location 72 hours after stopping treatment, the bleed is defined as a new bleeding episode.

CONFIDENTIAL

Date: Version: Status: Page:

23 October 2018 | Novo Nordisk 1.0 Final 6 of 16

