## 2.5 Interim analysis

The trial does not include a formal interim analysis. However, the split of the trial into a main and extension part offers the opportunity of reporting results before the end of the trial. For patients in

Statistical Analysis Plan		Date:	23 October 2018	Novo Nordisk
Trial ID: NN7415-4310	CONFIDENTIAL	Version:	1.0	
UTN: U1111-1179-2925	CONFIDENTIAL	Status:	Final	
EudraCT No : 2016-000510-30		Page.	13 of 16	

the concizumab s.c. prophylaxis arm, main part is defined to end when the last patient has completed a minimum of 24 weeks of treatment or at LPFT (visit 2) + 24 weeks if the last patient has withdrawn before visit 9. For patients in the on-demand arm, the main part consists of observations from randomisation until transfer to concizumab s.c. prophylaxis treatment or withdrawal from trial, whichever comes first. All observations for these patients after transfer to concizumab treatment is regarded as extension part of the trial. Other reporting of the trial might be done during the extension part once the data collection and review of the main part data has been finalised and individual clinical trial reports might in such case be issued. A clinical trial report describing results from the main and the extension part will be written when the last patient has either completed or withdrawn from the trial. All main conclusions regarding clinical proof of concept and dose guidance for phase 3 will be based on the reporting after the main part, see Figure 2–1.

[figure not shown]

Figure 2–1 Definition of main and extension part

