### 3.4 Offset definition for negative binomial regression for primary endpoint

Section 17.3.1 of the protocol defines the offset of the negative binomial regression as log of exposure time in the main period. For patients in the concizumab arm, this definition only accounts for the second CPoC criterion. The offset should reflect the observation period which differs for subjects in the concizumab treatment arm for the first CPoC which has been further clarified in section 2.3.1 of this document.

Section 17 of the protocol describes that the CPoC will be evaluated in a hierarchical fashion using two criteria to evaluate the effect of concizumab. The first CPoC criterion is evaluated using only a subset of observations where concizumab patients are at the last dose level reached at the time of analysis and excluding observations from the 2 weeks run-in period with 0.15 mg/kg. The second CPoC criterion is evaluated using all observations in the main part after randomisation.

The offset for first CPoC criterion of patients in concizumab arm is the log of the individual exposure time at the last dose level reached at the time of analysis excluding the 2 weeks run-in period for subjects on 0.15 mg/kg. The offset for the second criterion of patients in concizumab arm is the log of the individual exposure time in the main part. For both criteria and patients in the ondemand arm, the offset is the log of the exposure time in the main part.

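### The tipping-point analysis freezes the offset because missing time cannot be identified, yet for main-part exposure in the concizumab arm it can be, so one Delta means a different rate for each exit time

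*SAP*

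**What the plan says.** Section 2.3.2 plans a modified tipping-point analysis of the MAR assumption. It assumes a worse outcome for patients who stopped before the main part ended, and adds Delta to the main-part bleed counts of concizumab patients. "The offset is maintained as being the exposure during the main part", with the justification "since it is not possible to identify the amount of missing observation time". Delta is raised until superiority is lost. "The results of the primary analysis will be considered robust if the tipping point is above what is considered clinically plausible"; no number is set for plausible.

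Section 2 describes the main part as "defined to end when the last patient has completed a minimum of 24 weeks of treatment or at LPFT (visit 2) + 24 weeks". The second date applies when the final patient left before visit 9. Section 2.5 repeats this for the concizumab arm: "main part is defined to end when the last patient has completed a minimum of 24 weeks of treatment". In the on-demand arm the main part ends individually, at transfer to concizumab or withdrawal.

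The primary model in section 2.3.1 uses the "log of exposure time in the included observational period of the main part as offset". The same section then specifies: "The offset for first CPoC criterion of patients in concizumab arm is the log of the individual exposure time at the last dose level"; the run-in is left out. For criterion 2 it is exposure in the main part. Section 3.4 says of a main-part offset: "For patients in the concizumab arm, this definition only accounts for the second CPoC criterion".

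**The concern.** Two statements in the SAP do not fit together. Section 2.3.2 says the missing time is unknown. Sections 2 and 2.5 fix the date up to which a concizumab patient would have been observed in the main part, and the discontinuation date must be known to compute the patient's exposure at all.

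The consequence is practical. If bleeds are added and time is not, the same Delta is a large rate increase for a patient who left early and a small one for a patient who left late. The SAP then compares the tipping Delta with one notion of clinical plausibility. Early exits could make a sound result look fragile only because the offset was frozen.

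**Working it through.** **Inputs from the SAP.** Section 2: criterion met if the 95% confidence interval lies below 1. Section 2.1: 16 concizumab and 8 on-demand patients; on-demand ABR 24; over-dispersion 7 over 6 months; for criterion 2, ABR 7.6 over an average main part of 8 months (8/12 × 52 ≈ 35 weeks).

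**Assumed, because the SAP gives no dropout figures.** One to three concizumab leavers; exit at week 4, 8 or 20; main part of 35 or 24 weeks.

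**Model check.** The tipping-point section states no figure of its own, so the check is on the planning figures. For criterion 1 (ABR 6 vs 24, over-dispersion 7, 6 months), simulation gave 82.2% power against 82% in Table 2-1. For criterion 2, with concizumab followed for 35 or 24 weeks and on-demand for 24, 68-74% of simulated trials met the criterion, against about 70% in the SAP.

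**Step 1: missing time.** Missing weeks = T − t, where T is the patient's time from start to the trial-level end of the main part and t is the exit week. Both are known at analysis. With T = 35, exit at week 4, 8 or 20 leaves 31, 27 or 15 weeks missing.

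**Step 2: what one added bleed means.**
- Offset kept: the analysed rate rises by 52/t, that is 52/4 = 13, 52/8 = 6.5 and 52/20 = 2.6 per year.
- Time added: it rises by 52/T at every exit week, that is 52/35 = 1.5 or 52/24 = 2.2 per year.

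With the offset kept, Delta = 0 is MAR, but the same Delta differs fivefold (13/2.6) between exit at week 4 and week 20.

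**Step 3: effect on the tipping point.** 600 simulated data sets per scenario on the criterion 2 planning figures; negative binomial regression with common dispersion and Wald interval; the 409-445 data sets per scenario that met criterion 2 were kept. Offset kept: leaver's count + Delta, exposure to exit. Time added: leaver's count + fitted concizumab rate × missing time + Delta, exposure to the end of the main part. Delta is thus the excess over MAR in both, and goes to leavers only. Median smallest Delta at which the upper limit reaches 1:

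| Main part | Leavers | Exit week | Offset kept | Time added |
|---|---|---|---|---|
| 35 weeks | 2 | 4 | 4 | 18 |
| 35 weeks | 2 | 8 | 5 | 18 |
| 35 weeks | 2 | 20 | 10 | 17 |
| 24 weeks | 2 | 4 | 4 | 13 |
| 24 weeks | 2 | 8 | 6 | 13 |
| 24 weeks | 2 | 20 | 11 | 13 |
| 35 weeks | 1 | 4 | 6 | 30 |
| 24 weeks | 1 | 4 | 6 | 20 |
| 35 weeks | 3 | 4 | 3 | 14 |
| 24 weeks | 3 | 4 | 3 | 10 |

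The kept offset tipped no later in at least 99% of data sets in every scenario. Smaller repeat simulations agreed to within about 2 bleeds.

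**Step 4: the proposed scale.** With bleeds in the missing time imputed at the fitted rate times a multiplier (20 imputations, Rubin's rules, two leavers, 35 weeks, 89-92 data sets each), the median tipping multiplier was 5.5, 5.6 and 9.9 for exit at week 4, 8 and 20. At multiplier 1, 0-1% of data sets had already tipped.

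**The case against.** **The SAP's reason is partly right.** A reader might infer that missing time can be calculated for every offset. It cannot. How long a leaver would have stayed at the last dose level is not observed, so the criterion 1 offset needs an assumption. The on-demand arm has no common end date either, but it receives no Delta.

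**Criterion 1 may be covered.** Because the wording refers to main-part counts and exposure, which section 3.4 ties to criterion 2, one might infer that criterion 1 has no MAR check. The text does not establish that. The offset is said to be maintained and the conclusion concerns the primary analysis, so each criterion may be meant to keep its own offset. This is a wording gap.

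**Who receives Delta is not settled.** The opening sentence concerns patients who discontinued, but the next adds Delta to concizumab patients without that limit. Leavers only is the natural reading. If all concizumab patients received it, a small simulation (two leavers, 35 weeks) tipped at 4, 5 and 5 for exit at week 4, 8 and 20, and the dependence on exit week nearly disappears.

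**The rule is conservative.** This stands on the SAP's scale of bleed counts. One might infer that the error changes direction with exit week once Delta is turned into a rate, but that only arises from unlike denominators. Per year of missing time at 35 weeks, the kept offset tips at 4 × 52/31 = 6.7, 5 × 52/27 = 9.6 and 10 × 52/15 = 34.7. With time added, it tips at 18 × 52/31 = 30, 18 × 52/27 = 35 and 17 × 52/15 = 59. The kept offset is lower throughout. Conservatism does not make Delta interpretable, however.

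**The multiplier is not invariant.** Correct: 5.5, 5.6 and 9.9. It has a clear meaning, but still depends on how much time is missing.

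**Conclusion.** The concern holds in a limited form. For the concizumab arm's main-part exposure, the stated reason for freezing the offset contradicts sections 2 and 2.5. If Delta goes to leavers only, its meaning varies fivefold between exit at week 4 and week 20, and it cannot be judged against one plausible value. In bleed counts the analysis tips too early, against concizumab. The gap is large for early exits (4 vs 18 with two leavers at week 4 and a 35-week main part) and small for late exits from a 24-week main part (11 vs 13).

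The sizes rest on assumed numbers of leavers, exit weeks and main-part lengths, and on the planning rates and over-dispersion. The point is moot if no concizumab patient discontinues. The proof-of-concept decision is unchanged, and a result that survives a large Delta under the planned rule remains valid evidence of robustness. The plan should be changed, but the primary analysis is not affected.

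**What to change.** In section 2.3.2:

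1. State that the worsening applies only to concizumab patients who discontinued.
2. Drop the statement about missing time for main-part exposure. Add each leaver's missing time (main-part end date minus discontinuation date) to the offset.
3. Impute bleeds for that time at the fitted concizumab rate times a multiplier, with 1 corresponding to MAR. Raise the multiplier until the 95% confidence interval reaches 1.
4. Report the tipping multiplier together with the amount of missing time.
5. State that the analysis is run for both criteria, each with its own counts and offset. For criterion 1, state the assumption that missing time is counted at the last dose level reached.

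The cost is SAP wording, a short imputation program and one untestable assumption for criterion 1. No new data are needed.

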### 2.3.3 Additional analysis

An additional evaluation of the primary endpoint will be made, including actual concizumab dose level (interpreted as the patient's last dose level) as additional factor in the primary analysis model specified above. Point estimates and 95% confidence interval will be provided for the ABR at the different dose levels of concizumab (0.15, 0.20 and 0.25 mg/kg). Furthermore, a series of analyses with individual steady state PK/pharmacodynamics (PD) assessments included as log-transformed covariates in the negative binomial regression model as specified for the primary analysis will be performed in order to evaluate possible associations between PK/PD and ABR that potentially could guide dose-selection. The referred steady-state PK/PD assessments comprise the concizumab

Statistical Analysis Plan		Date:	23 October 2018	Novo Nordisk
Trial ID: NN7415-4310	CONFIDENTIAL	Version:	1.0	
UTN: U1111-1179-2925	CONFIDENTIAL	Status:	Final	
EudraCT No.: 2016-000510-30		Page:	10 of 16	

trough level at visit 9, maximum plasma concentration ( $C_{max}$ ) of concizumab throughout the trial, tissue factor pathway inhibitor (TFPI) value prior to the last s.c. dose administration, peak thrombin generation (nM), Endogenous thrombin potential (nM\*min) and velocity index (nM/min) prior to the last dose administration at 24 weeks. This model will only include observations from subjects exposed to concizumab.

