# Clinical proof of concept

The statistical analysis of the collected data aims to establish clinical proof of concept (CPoC) that concizumab is efficacious in preventing bleeding episodes in haemophilia patients with inhibitors. The objective will be assessed when the last of the 24 patients has completed 24 weeks of dosing (or has withdrawn before that).

Two criteria will be evaluated in a hierarchical fashion in support of CPoC comprising a comparison of the annualised bleeding rate (ABR) of all patients in the concizumab group, irrespective of individual dose titration, with the ABR of the patients in the on-demand arm using different sets of observations. The primary CPoC criterion aims at evaluating the effect of concizumab when given at the last dose level reached for the patient. Hence, for this evaluation, only observations from the period where patients are on their end dose at time of analysis will contribute to the analysis. Furthermore, observations from the 2 week run-in period will not be included. Since this evaluation disregards a subset of data collected post randomisation, the result should be viewed taking into account the potential bias. The second CPoC criterion aims at evaluating the effect of concizumab when given as an escalation regimen. Hence, this will compare the ABR of patients in the concizumab arm with the ABR of the patients in the on-demand arm using all data collected after randomisation. The second CPoC criterion will only be evaluated if the first one succeeds.

The referred comparisons will be made using a negative binomial model with log of exposure time in main part as offset and regimen as factor (concizumab vs. on-demand). For each criterion, evidence of effect will be concluded if the 95% confidence interval of the treatment ratio is below 1.

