### Clinical arguments for the hierarchical test approach

Concizumab exhibits non-linear pharmacokinetics (PK) due to target mediated drug disposition and it is expected that the dose response curve of the ABR is rather steep. This implies that patients that are on a dose which is not efficacious are likely to bleed as patients that are not treated at all. The subset of data collected from the last dose clinically deemed as efficacious would reflect the efficacy of concizumab in the given patient.

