#### 2.1 Sample size calculation

The estimand will be defined as the "if all patients had adhered" estimand.

The treatment ratio between prophylactic s.c. concizumab and on-demand intravenous (i.v.) eptacog alfa (rFVIIa) during at least 24 weeks for all randomised patients if all patients adhered to trial drug and did not initiate alternative treatment options.

Statistical Analysis Plan	CONFIDENTIAL	Date:	23 October 2018	Novo Nordisk
Trial ID: NN7415-4310		Version:	1.0	
UTN: U1111-1179-2925		Status:	Final	
EudraCT No.: 2016-000510-30		Page:	7 of 16	

This estimand is a de jure estimand assessing the expected added benefit a patient can achieve if continuing treatment with prophylactic s.c. concizumab as compared to on-demand i.v. eptacog alfa (rFVIIa) under similar conditions as observed in this trial.

The sample size calculation has been determined based on this estimand and the CPoC criteria taking the small patient population into account, while also aiming for an acceptably narrow 95% confidence interval for the rate ratio.

Sufficient inference on bleeding episodes for the primary CPoC criterion is judged to be accommodated by 16 patients in the concizumab arm and 8 in the comparator arm. It is expected that the treatment duration of the main part allowing for escalation time for some patients is on average 6 months in the below calculations.

When evaluating the power of the negative binomial analysis referred above, annual bleeding rates of 24 and 6 are assumed for the on-demand patients and the end dose concizumab regimen, respectively. Assuming further over-dispersion of 7, the power for concluding superiority of the concizumab regimen becomes approximately 80%. The power under varying values of true ABR and over-dispersion for the primary CPoC criterion are shown below in Table 2–1.

Table 2-1 Power in superiority comparison between concizumab prophylaxis and on-demand treatment under different assumptions of ABR for concizumab and overdispersion (assuming on-demand ABR=24).

Power	Over-dispersion (over 6 months)			
ABR (concizumab)	6 7 8			
6	89%	82%	75%	
7	84%	75%	70%	
8	77%	69%	66%	

For the secondary CPoC criterion that includes data prior to potential dose escalation, it is expected that the treatment duration of the main part is on average 8 months with an average ABR of 7.6 for the concizumab regimen. This yields a marginal power of approximately 70% for the secondary CPoC criterion.

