## 2.4 Supportive secondary endpoints

# 2.4.1 Supportive secondary efficacy endpoints

- The number of bleeding episodes during 76 weeks from treatment onset
- The number of spontaneous bleeding episodes during at least 24 weeks from treatment onset
- The number of spontaneous bleeding episodes during 76 weeks from treatment onset

The number of spontaneous bleeding episodes during at least 24 weeks from treatment onset will be addressed in terms of the same estimand as for the primary endpoint. The estimand will be estimated using the same negative binomial regression model as for the primary endpoint and performing the same two analyses as for the primary endpoint; one only including observations from the period on the last dose level for patients treated with concizumab and one including the entire escalation regimen.

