### 3.6 Additional analyses for primary endpoint

Section 17.3.3 of the protocol describes the additional analyses of the primary endpoint. Section 2.3.3 of this document clarifies how the additional analysis including actual concizumab dose level as factor in the primary analysis model should be interpreted as including the patient's last dose level as factor in the primary analysis. The section also clarifies how the series of additional analyses will be performed with each of the PK/PD variables taken prior to last dose at 24 weeks.

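### Annualised bleeding rates (ABRs) reported by last dose level describe who ended at each dose; if escalation follows bleeding, they do not estimate the ABR at that dose

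*SAP*

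**What the plan says.** SAP 2.3.3 (Additional analysis) puts the dose level into the primary model, reads it as the patient's last dose level, and promises that "Point estimates and 95% confidence interval will be provided for the ABR at the different dose levels of concizumab", namely 0.15, 0.20 and 0.25 mg/kg. SAP 3.6 confirms this reading of the "additional analysis including actual concizumab dose level as factor in the primary analysis model".

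The dose is not randomised within the concizumab arm. The section on clinical proof of concept (CPoC) compares the whole arm with on-demand treatment "irrespective of individual dose titration". The clinical arguments for the hierarchical approach say: "The subset of data collected from the last dose clinically deemed as efficacious would reflect the efficacy of concizumab in the given patient". They also expect a steep dose response, in which "patients that are on a dose which is not efficacious are likely to bleed as patients that are not treated at all".

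SAP 2.3.1 fits the model with "log of exposure time in the included observational period of the main part as offset" and defines two such periods for concizumab patients: time at the last dose level, and the whole main part. For spontaneous bleeds, SAP 2.4.1 says that both are used: "one only including observations from the period on the last dose level for patients treated with concizumab and one including the entire escalation regimen". SAP 2.3.3 does not say which applies to the dose-level ABRs.

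The CPoC section warns of possible bias for the first criterion, because that criterion drops post-randomisation data. SAP 2.3.3 carries no such warning.

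**The concern.** The output is worded as the ABR at a dose, but the model estimates the ABR of the patients who ended at that dose. These differ if a patient moves up because of bleeding, and two selection effects then act. Patients who remain at 0.15 had few bleeds in the same period that is analysed. Patients who reach 0.25 tend to have a high underlying rate whatever the dose does. The model-based confidence intervals reflect sampling error only and allow for neither effect.

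A reader who takes the table at face value could see the lowest level as best when the levels are equal, or when higher levels bleed less. SAP 2.5 bases the phase 3 dose guidance on the main-part reporting, and this table is part of that reporting.

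**Working it through.** **The plan's own figures.** The SAP gives no expected ABR by dose level, so none can be reproduced. Its power figure does confirm how over-dispersion is meant. With 8 and 16 patients, 6-month means of 24/2 = 12 and 6/2 = 3, and a variance-to-mean ratio of 7, the standard error of the log rate ratio is sqrt(7/(8×12) + 7/(16×3)) = 0.468, which gives 84.2% power. Simulating the planned regression gives 82.3%, against 82% in Table 2-1.

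**Patient heterogeneity.** With a gamma patient effect of variance k, over-dispersion is 1 + k × mean. Setting this to 7 gives k = 6/12 = 0.5 at the on-demand mean and k = 6/3 = 2 at the concizumab mean. I use k = 0.5 to 2.

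**Is escalation linked to bleeding?** The sentence on the dose clinically judged efficacious supports a link. SAP 2.1 expects an ABR of 6 at end dose over 6 months, and for the second criterion a duration "on average 8 months with an average ABR of 7.6 for the concizumab regimen". If the 8 months contain the 6, the ABR before the end dose is (8×7.6 − 6×6)/2 = 12.4. That fits bleeding-linked escalation, but fits equally well a true dose response with escalation on any other basis.

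**Simulation.** Assumptions not in the SAP: escalation after 3 bleeds in 12 weeks, main part of 24 to 45 weeks, and run-in excluded from the trigger and from the count. Bleeds and exposure are taken at the last dose level only. Ranges show variation between separate codings of the same assumptions.

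| True ABR at 0.15/0.20/0.25 | Reported, k = 0.5 | Reported, k = 2 |
|---|---|---|
| 6/6/6 | 2.6 / 4.3 / about 12 | 1.4 / about 4.5 / about 20 |
| 12/6/3 | 3.1 / 3.6 / 5.4–5.7 | 1.6 / 3.6 / 8.6–9.7 |
| 24/6/1.5 | 3.4 / 3.2 / 2.6 | 1.6 / 2.9 / 4.1–4.5 |
| 24/12/6 | 3.4 / 4.1 / 9.1 | 1.6 / 3.8 / 14.5 |
| 6/6/6, dose unrelated to bleeding | 6.0 / 6.0 / 6.1 | not needed |

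The first three truths give a pooled end-dose ABR of about 2.6 to 4.0, below the 6 planned in SAP 2.1. The truth 24/12/6 gives about 6.3 to 6.6 and so comes close to the planned scenario. Its order is reversed.

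**Other triggers.** With 2, 3 or 4 bleeds in 8 or 12 weeks, 24 weeks of follow-up and equal true ABRs of 6, the reported ranges are 0.9–2.8, 2.8–10.3 and 19.7–30.9. With true effects of ×0.7/×0.5 or ×0.5/×0.25 relative to 0.15, the order was reversed under every one of these triggers.

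**Observation period.** The period matters. Over the whole main part, 24/6/1.5 appears as 3.4/7.5/11.6 (k = 0.5) to 1.6/7.3/13.7 (k = 2), clearly reversed, whereas the last-dose period at k = 0.5 only flattens it.

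**Analysis by dose in force.** A Poisson model with current dose as factor and a gamma patient effect returns, at k = 0.5 and k = 2, 6.0/6.0/6.0 and 6.1/6.0/6.1 for 6/6/6; 12.0/6.0/3.0 in both cases for 12/6/3; and 24.0/6.0/1.5 and 23.9/6.0/1.5 for 24/6/1.5. I also tried a threshold truth, in which a dose either works in a patient (ABR 6) or does not (ABR 24), and 40/30/30% of patients respond from 0.15/0.20/0.25. The true ABRs are then 0.4×6 + 0.6×24 = 16.8, 0.7×6 + 0.3×24 = 11.4, and 6.0. The model returns 15.2/9.2/4.8 and 14.9/9.1/5.4, which is too low but in the right order.

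**The case against.** The SAP says openly that dose level means last dose level, calls the analysis additional, and attaches no dose-comparison test or causal claim to it. The escalation rule is presumably in the protocol, and if it does not depend on bleeding there is no bias. The observation period can be read as both periods, by analogy with SAP 2.4.1. The alternative model has weaknesses of its own.

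Much of this stands, and it limits the point to wording plus one supportive analysis. It does not remove the point: the promised output is an ABR and interval at a dose, and the one sentence in the SAP that characterises the last dose ties it to judged efficacy.

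A reader might infer more than the document supports:

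- That the mention of individual titration, or the 12.4 derived from SAP 2.1, proves a bleeding-based trigger. Both are only compatible with one.
- That the dose order is always reversed. Under the very steep effect 24/6/1.5, with bleeds counted at the last dose, it is flattened at k = 0.5 and reversed at k = 2.
- That phase 3 dose selection rests on this table. SAP 2.5 names the main-part reporting, not this analysis, and the remark in SAP 2.3.3 about guiding dose selection belongs to the pharmacokinetic and pharmacodynamic models.
- That proof of concept is compromised. Neither criterion uses the dose-level factor.

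**Conclusion.** The point holds conditionally. If escalation is linked to bleeding, as the clinical arguments suggest, the ABRs and intervals by last dose level mix patient selection with dose effect and do not estimate the ABR at a dose. Under the assumed trigger, equal levels can look about five-fold apart (12/2.6 = 4.6) at k = 0.5 and about fourteen-fold apart (20/1.4 = 14.3) at k = 2. A moderate true benefit is reversed, including in the scenario closest to the planned end-dose ABR.

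The sizes rest on the assumed trigger, follow-up and gamma heterogeneity. The direction was stable across the triggers tried, except that the very steep effect was only flattened at k = 0.5. This is an inexpensive improvement to an additional analysis.

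**What to change.** In SAP 2.3.3:

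1. Label the ABRs by last dose level as descriptive for patients ending at that level and as confounded by titration, and extend the bias caveat from the CPoC section to them.
2. State which of the two observation periods in SAP 2.3.1 applies, or that both do.
3. Add a supportive analysis by dose in force. Split each concizumab patient's main-part follow-up after the 2-week run-in by current dose. Model treated bleeds per dose period with log exposure as offset, current dose level as factor (on-demand, 0.15, 0.20, 0.25 mg/kg) and a gamma patient effect. Report the ABR and 95% interval per level. State the assumptions: escalation depends only on recorded bleeds, the patient effect is gamma, and the dose effect is a common multiplier. The run-in is left out because SAP 2.3.2 notes that some patients could stay on their earlier prophylaxis then.

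Items 1 and 2 are the minimum and cost only wording. Item 3 costs one model, and the bleed and dose dates it needs are already required for the first CPoC criterion. Its limits should be stated. Intervals are wide with 16 patients: with no true dose effect, the 0.25/0.15 ratio spans about 0 to 2.9 (k = 0.5) or 0.16 to 2.4 (k = 2) in 95% of simulated trials. Levels are about 10 to 25% too low if response is a patient-specific threshold. A wrong shape for the patient effect can shift a single level by up to about 22%, and escalation on grounds other than recorded bleeds would leave some bias. No dose or titration rule is proposed.
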